Clinical Global Impressions-Improvement Scale (CGI-I)			X	X	X	X	X	X	X	X
Clinical Global Impressions-Baseline		X								
Adverse Events Check-in		X	X	X	X	X	X	X	X	X

*Administered twice per visit, immediately before and immediately after LFMS treatment.

Safety Procedures

h. Suicidality Procedures

Suicidal ideation (SI) is not uncommon in people suffering from GBD. Suicidality will be assessed throughout the study during the screening visit, treatment visits and follow-up visits. Using the C-SSRS. The GPMADOC suicidality SOP will be prompted by over threshold responses for certain items on mood rating scales or by spontaneous report of suicidal ideation at any time. Specifically,

- The use of the GPMADOC Suicidality SOP will be triggered by spontaneous report of suicidal ideation or by over-threshold responses to specific items on mood ratings.
- The Suicidality SOP instructs the use of the C-SSRS and uses the responses to questions 4 and 5 as a threshold for physician involvement. If the responses to these two questions are “yes” then the study physician will be contacted for in-person assessment or for phone call-back assessment as appropriate. The C-SSRS will be completed while awaiting the physician.
- The following mood rating items and thresholds trigger use of the Suicidality SOP: C-SSRS, “yes” to questions 4 and 5; MINI, “yes” on items B7, B9 or B10; MADRS, 4 or 6 on item 10.

We note that the CGI is used for withdrawal criteria, but this scale is not used for suicidality assessment, but rather to ensure safe continuation of the study.

i. Medication or Therapy Changes

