During the screening visit, a trained clinical study staff member will interview and assess the subject using the Screening Measures, during which a detailed medical history will be obtained and current medications noted. Suicidality risk is assessed as part of the Safety Measures; a positive response to items 4 or 5 of the C-SSRS will prompt the use of the Suicidality SOP.

A urine drug screen and, if female, a pregnancy test will be performed. Subjects will be accepted for the treatment trial based on the interview and review of results by a study physician.

The screening visit, including the rating scales and physical exam, will take approximately 2 hours and will be done up to one week before the baseline visit. If subjects meet study criteria after the screening visit, a baseline visit will be scheduled.

Baseline (Visit 2) Procedures

Contingent on a successful screening visit, subjects will come in for a baseline visit on the Thursday or Friday prior to the 5 days of consecutive LFMS treatment. This visit will take about 1 hour to complete. Subjects will be administered Long- and Short-Term mood scales as well as the Safety Measures. A positive response to items 4 or 5 on the C-SSRS will prompt the use of the Suicidality SOP (see ‘Suicidality Procedures’ above).

LFMS (Visits 3-7) Procedures

Subjects will come in for 5 daily consecutive LFMS treatments over a period of five days, Monday-Friday. If subjects are unable to come in for five consecutive days due to a scheduling conflict, we will accept a schedule of four consecutive days without considering this a protocol deviation. Women of childbearing potential will be required to complete a urine pregnancy screen at screening and before each LFMS procedure.

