The Safety Measures will be administered. As part of these, the C-SSRS will be used as a suicidality risk assessment and any positive response to items 4 or 5 will prompt the use of the Suicidality SOP (see ‘Suicidality Procedures’ above). The second part of the Safety Measures is the CGI-I, which will be used to ensure safe continuation of the study; a score of 6 or more will prompt a consultation with the study physician and potential withdrawal from the study (see “Withdrawal Criteria” above). Medication and/or treatment changes will be asked about and noted. Changes in treatment will not prompt withdrawal but will indicate that data will be excluded from analysis (see “Medication and Therapy Change Procedures” above). A brief progress note will be recorded. The Short- and Long-Term mood scales will be

Low Field Magnetic Stimulation: Initial Trial in Geriatric Bipolar Depression

administered, and LFMS procedures will begin immediately after these mood ratings are completed. HARS and MADRS Long-Term mood scales will only be administered on Visits 3, 5, and 7.

Randomization occurs automatically when the subject number is entered on the LFMS Device during the first treatment visit.

For LFMS procedures, the subject will lie down on the patient table with his/her head positioned inside the device cylinder, and the operator will start the LFMS device. The device has been designed so that the cylinder does not extend below the eyes in order to reduce claustrophobia. Subjects will be instructed to remain silent during the treatment, except in cases of discomfort, desire to discontinue treatment, or similar situations related to subject safety and study participation. Subjects will be given one 20 minute exposure to either the LFMS or sham electromagnetic field treatment. Subjects will be told they may receive either the active treatment or a sham, inactive treatment.

After treatment, the Short-Term Measures will be completed again to obtain post-treatment scores. Subjects will also be asked about possible side effects or sensations. After the treatment and mood ratings, subjects may leave immediately or rest in the Imaging Center waiting area until they are ready to leave or return to the GPMADOC and the SAGE Program, located in South Belknap.

Follow-up Visit (Visit 8)

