Due to the nature of affective disorders, it is possible that a subject may develop or experience an increase in suicidal ideation during their participation in the study. If it is determined that a subject has developed increased suicidal thinking, either through increased scores on the or through conversation with clinical study staff, a study physician and the subject's clinician will be called immediately.

e. Drug side effects and toxicities

N/A

f. Device complications/malfunctions

Risks Related to LFMS Device

LFMS technology does not use ionizing radiation. Instead, it uses electric field pulses that may stimulate the brain. There are no known hazards or risks associated with this technique. The LFMS device, unlike an MR scanner, has no permanent magnet and thus has no magnetic field when not in active operation. During treatment there is a small, low frequency magnetic field near the device. This field is less than 5 Gauss when further than 1.5 feet from the device. We plan to be conservative and follow the 5 Gauss guidelines for MRI sites and place a magnetic area sign in the doorway during treatment sessions, to warn anyone who may enter the room during the 20 minute treatment. Outside of the treatment time, there are no fields and thus no safety issues.

Persons with pacemakers, neurostimulators, or metal in head or neck will not be enrolled or allowed in the room during device operation.

Low Field Magnetic Stimulation: Initial Trial in Geriatric Bipolar Depression

There is a red button on the device that can be manually pushed in the event of a hardware failure or an emergency. This mechanically disconnects the coil from the power source and dumps the energy stored in the coil safely to a heat dissipative resistor. If the subject asks to terminate the experiment or experiences a medical emergency, there is a “stop” button on the interface that can be clicked with the computer mouse, and this will stop waveform execution.

Risks Related to Pregnancy

There are no known risks for pregnancy associated with this type of electromagnetic field exposure. However, in order to ensure subject safety, women who are pregnant, as confirmed by pregnancy test, will be excluded from this study.

Radiation Risks (statement provided by Radiation Safety Committee)

N/A

VIII. POTENTIAL BENEFITS

b. Potential benefits to participating individuals and/or to society

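### Section VII has a study physician and the subject's clinician called whenever increased suicidal thinking is determined; Suicidality Procedures (V.h) ties physician contact to C-SSRS questions 4 and 5 and does not name the clinician

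*Combined protocol and SAP*

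**What the plan says.** **Section VII (Phase 2, VII.d, Psychosocial risks; same in Phase 1, VII.a).** The rule begins "If it is determined that a subject has developed increased suicidal thinking". It gives two routes to that finding: higher scores on a scale, whose name is absent from the text, "or through conversation with clinical study staff". The action names two people, a study physician and the subject's own clinician. It ends "clinician will be called immediately". No C-SSRS threshold is attached to the conversation route.

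**Suicidality Procedures (Phase 2, V.h; same in Phase 1, V.a).** The SOP is started by certain scale responses or "by spontaneous report of suicidal ideation at any time". The SOP then applies the C-SSRS and "uses the responses to questions 4 and 5 as a threshold for physician involvement". If those answers are yes, "then the study physician will be contacted for in-person assessment or for phone call-back assessment as appropriate". The section does not list the subject's clinician as someone to contact, and it does not mention VII.

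**Visit sections (Phase 2).** The baseline section says "A positive response to items 4 or 5 on the C-SSRS will prompt the use of the Suicidality SOP". The treatment-visit section says "any positive response to items 4 or 5 will prompt the use of the Suicidality SOP", and the Visit 8 section does the same. All three point to Suicidality Procedures. The phone-call section names the SOP on a positive answer to either question.

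**The concern.** Both sections deal with suicidal thinking that emerges during the study, and they attach different actions to it. VII acts on the finding itself. V.h adds a condition before a physician is involved, and leaves out the second person whom VII names.

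The case that matters is a subject who tells staff that suicidal thoughts have appeared or worsened, is judged to have increased thinking, and answers no to C-SSRS questions 4 and 5. Staff working from V.h find that its condition for contacting the physician is not met. They also find no instruction about the treating clinician, so they could omit two calls that the protocol promises elsewhere.

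Subjects with dangerous or active ideation are excluded at entry, so ideation that emerges later is what VII is there to catch. V.h itself describes suicidal ideation as not uncommon in this population. Phase 2 also requires each subject to have a treating psychiatrist within 2 hours of the hospital, so there is a clinician to call.

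**Working it through.** The plan gives no figure to reproduce. The check sets the two rules side by side and counts the calls that each one states.

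**Inputs**
- VII, once an increase is determined: study physician and subject's clinician, so 2 calls.
- V.h, after a spontaneous report: study physician only, and only if the answers to C-SSRS questions 4 and 5 are yes.

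**Comparison, given that an increase has been determined through conversation**

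| C-SSRS questions 4 and 5 | Calls in VII | Calls in V.h | Difference |
|---|---|---|---|
| No to both | 2 | 0 | 2 − 0 = 2 |
| Yes to one only | 2 | 0 or 1 | 2 or 1 |
| Yes to both | 2 | 1 | 2 − 1 = 1 |

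The middle row is uncertain because V.h refers to both questions being answered yes, while the visit sections use either question. In every row V.h leaves out the subject's clinician.

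**Does another provision supply both calls?**
- *Withdrawal criteria (Phase 2, III.e; Phase 1, III.b):* dangerous or active ideation is judged from the C-SSRS, the suicide-related questions on the MADRS (and on the BDI in Phase 1) and a study clinician's opinion. This decides removal from the study and does not mention the subject's own clinician.
- *CGI-I of 6 or more (treatment-visit sections):* this prompts consultation with the study physician, but V.h says that the CGI is not used to assess suicidality.
- *Help for a subject upset by the questions (VII.d):* a study physician is available. The trigger is different, and only one person is named.
- *Adverse event reporting (Phase 2, IX.f):* events related to study procedures go to appropriate clinicians. This is again a different trigger.

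None of these states both calls on a finding of increased suicidal thinking.

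**Would the fix need new data?** No. The Phase 2 schedule has the C-SSRS at 8 visits and 2 phone calls, which is 10 of 10 contacts. Phase 1 has it at 9 of 9 visits.

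**The case against.** The strongest reply is that the sections are compatible. V.h summarises what the SOP does, VII adds a duty, and nothing in V.h forbids a call. This stands: VII is binding, and staff who apply both sections would make both calls. A reader might infer that V.h tells staff to call nobody when the answers are no. The documents do not support that, because V.h is silent on the point and gives no such instruction. What remains is that V.h labels its step a threshold for physician involvement, and VII has no such threshold.

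A reader might also infer that the visit sections steer staff away from VII, since three Phase 2 sections (two in Phase 1) point to Suicidality Procedures and none to VII. That count is no evidence for the no/no case. Those pointers apply only when question 4 or 5 is positive, so with two negative answers staff reach V.h through its own spontaneous-report trigger.

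Two further limits stand. The full SOP is not among the documents and may already require contact with the subject's clinician, so a gap in practice is not shown. The triggers also differ: V.h starts on any spontaneous report, whereas VII starts once an increase is determined, and the C-SSRS may be part of that determination. The comparison therefore covers only subjects for whom the determination has been made.

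Finally, VII might seem to require both calls for every scale item listed in V.h. The scale name is missing from VII, so this cannot be established. The MINI items are rated only at screening, with no earlier study rating against which to judge an increase.

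**Conclusion.** The point holds as a mismatch between two stated safety rules, and it should be corrected. Once increased suicidal thinking has been determined, V.h states 2 fewer calls than VII if both C-SSRS answers are no, and 1 fewer if both are yes. The same holds in both phases.

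This rests on reading V.h by itself, on the conversation route in VII (so the missing scale name does not matter), and on the determination having been made. It does not show that any subject would go without a call. The documents give no frequency for such cases, and none is estimated here. Confidence is medium, mainly because the SOP could not be read.

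**What to change.** First check the full SOP. Then add to V.h, and to the SOP if it differs, wording such as:

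> Whenever new or increased suicidal thinking is determined, including by spontaneous report or conversation, the study physician and the subject's clinician are called immediately (see VII), whatever the answers to C-SSRS questions 4 and 5. Those answers set the urgency and form of the physician's assessment.

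Do not extend the two calls automatically to every listed scale item. For those items, keep the existing SOP trigger unless an increase is determined. It would help if the study physicians defined new or increased thinking, for example against the C-SSRS at the previous contact.

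Narrowing VII to V.h's threshold would also make the sections agree, but it would withdraw a protection that the protocol already states.

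The cost is a short text change and no new assessment. The downside is some extra phone calls, all of which VII already requires; the documents do not allow an estimate of how many.

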- Hypothesis 2: We hypothesize that subjects will show long-term improvement over one week in anxiety following the first LFMS experimental treatment, as measured by the Hamilton Anxiety Rating Scale (HARS).

Aim 3: To assess any cognitive benefits from regular LFMS in older adults suffering from bipolar depression.

Low Field Magnetic Stimulation: Initial Trial in Geriatric Bipolar Depression

- Hypothesis 3: We hypothesize that subjects will show cognitive improvement, as measured by the Repeatable Battery for the Assessment of Neuropsychological Status (RBANS), at the follow-up visit as compared to baseline.

III. SUBJECT SELECTION

Up to 64 subjects will be enrolled in order to achieve our target of 32 completers of the treatment protocol. Subjects will be referred by clinicians from the Division of Geriatric Psychiatry at McLean Hospital.

d. Inclusion/Exclusion criteria

Inclusion criteria:

6. Subjects will be men or women aged 55 years or older.
7. Subjects will have a diagnosis of Bipolar Disorder Type I or II, current episode depressed as measured by a MADRS ≥ 20 .
8. Subjects must be maintained on a stable dose of all psychotropic medications for a period of at least two weeks prior to screening.
9. Subjects must be capable of providing informed consent.
10. Subjects must live within 2 hours of McLean Hospital.
11. Subjects must have a treating psychiatrist within 2 hours of McLean Hospital.

Exclusion criteria:

8. Dangerous or active suicidal ideation.
9. Subjects meeting DSM-V criteria for any Axis I disorder other than Bipolar Disorder or an anxiety disorder (e.g. Major Depressive Disorder, dementia).
10. Subject has an MMSE score ≤ 24 .
11. Subject is pregnant or plans on becoming pregnant.
12. Subject has recent history (within 7 days of screening) of ECT or TMS treatment.
13. Subject has recent history of substance abuse (cannot meet DSM-V criteria for substance abuse, no significant drug abuse within last 3 months, no history of dependence in last year, no drug use within last month, other than marijuana use).
14. Subject is experiencing active psychosis as determined by “yes” answers to questions K12 and K13 in the Mini International Neuropsychiatric Interview (MINI).
15. Subject has any contraindication for MRI (i.e. Presence of a pacemaker, neurostimulator, or metal in head or neck).

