programs will identify patients from their group that may be potential subjects. We have also obtained permission from the clinical directors of these programs to have a research coordinator look through electronic patient charts using Epic to identify eligible subjects. Once a potential subject has been identified, study staff will discuss the possibility of study participation with the patient's doctor and/or case manager to determine if the study would be appropriate. Potential subjects may be given an informational flyer about the study by clinical staff. The clinicians and staff members will not discuss aspects of the study with potential subjects so as to prevent the patient from experiencing undue pressure from their provider. We expect that potential subjects may be confused and/or upset if they were contacted by research staff at McLean without prior knowledge. Therefore, involving clinical staff as the first point of contact is essential to bridge patient communication between the two institutions. Clinicians will not be required or pressured to enroll patients in the study and patients' routine clinical care will not be jeopardized in any way if they choose not to participate. Potential subjects will be told that participation is completely voluntary and can be terminated at any time, for any reason by the patient.

A clinical research study staff member will contact interested and viable study candidates to explain the study procedures, answer any questions that the potential subject may have and conduct a pre-screening interview over the phone. Pre-screen interviews will be reviewed with the principal investigator on a weekly basis. Potential subjects who pass the pre-screen interview and are still interested in the study will be scheduled for an informed consent and prescreening visit at McLean Hospital.

Acceptance will rely on approval by one of the study physicians, in addition to satisfying all other criteria.

Subjects will be paid \$30.00 for each visit (not including phone follow-ups) to help cover the cost of travel and meals. Subjects may earn a maximum of \$240.00 over the course of the 8 visits.

IV. SUBJECT ENROLLMENT

d. Methods of enrollment, including procedures for patient registration and/or randomization

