A clinical study staff member will contact potential subjects to explain the study procedures and answer any questions that potential subjects may have. If potential subjects are interested, treatment visits will be scheduled.

e. Procedures for obtaining informed consent (including timing of consent process)

Informed Consent will be obtained by either a doctoral-level psychologist or by a CITI certified research assistant. If a research assistant obtains Informed Consent then a study psychologist will be available on site as back-up during the consent process, and subjects will be offered the option of speaking with a study psychologist or physician before consenting. The PI will also be available to answer questions if requested by the subject. Any discussion with additional study staff will be recorded in the consent log. Informed Consent will be obtained using an informed consent for approved by the Partners Healthcare IRB.

Subjects will be given ample time to review study procedures before consenting and will receive a copy of the signed consent document to keep. Consent will be signed under conditions that give free power of choice without intervention or undue duress, persuasion, coercion, or deception. The clinical study staff will sign the consent after confirming the subject understands the conditions of participation. Signed consent forms will be stored in a locked filing cabinet in a locked office.

f. Treatment assignment, and randomization (if applicable)

This is a randomized, double-blind, sham-controlled study. There is no physical sensation associated with the treatment, and all operating sounds are duplicated during sham, so that the operator, rater, and subject are all blinded. An inaccessible log file records the treatment condition, time and date of each system use for confirmation after the study is un-blinded.

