Subjects will be distributed equally into two groups. One group will receive active LFMS during the treatment week and the other group will receive sham LFMS during the treatment week. Treatment assignments will be randomized and balanced within blocks of 10. Randomization is performed automatically on the first treatment visit. The LFMS Device contains a pre-randomized folder of subject treatment links that are assigned to subjects as they arrive for their first treatment. This list was randomized in ten-subject blocks at the start of the study (using a random number generator). This randomization schedule has since been updated to reflect the parallel-group, 5-day design of this protocol.

V. STUDY PROCEDURES

Study Overview

b. Study visits and parameters to be measured (e.g., laboratory tests, x-rays, and other testing)

This study will consist of a screening visit; a baseline visit; we will aim to administer four or five daily LFMS treatment or sham treatment visits over a period of five days and one in-person follow-up visit for ratings on the Monday after the treatment week. If a subject is unable to attend only one treatment visit in the five day window, this will not be considered a protocol violation. Follow-up rating scales will be administered by phone once per week for two weeks following the last visit.

Visits and Procedures	Screening	Baseline	LFMS experimental treatment					Follow-Up Visit	Follow-Up Phone Call	Follow-Up Phone Call
	Visit 1	Visit 2	Visit 3	Visit 4	Visit 5	Visit 6	Visit 7	Visit 8		
LFMS			X	X	X	X	X			
M.I.N.I International Neuro-Psychiatric Interview (MINI)	X									
Cumulative Illness Rating Scale (CIRS-G)	X									
Mini-Mental State Exam	X									
Repeatable Battery for the Assessment of Neuropsychological Status (RBANS)		X						X		
LFMS Demographics Form	X									
LFMS Medical Screening Form	X									
LFMS Medications Form	X									
Drug Test	X									
Pregnancy Test	X		X	X	X	X	X			
Montgomery-Asberg Rating Scale (MADRS)	X	X	X		X		X	X	X	X
Hamilton Anxiety Rating Scale (HARS)		X	X		X		X	X	X	X
Positive and Negative Affect Schedule (PANAS)*		X	X	X	X	X	X	X	X	X
Young Mania Rating Scale (YMRS)	X	X	X	X	X	X	X	X	X	X

Low Field Magnetic Stimulation: Initial Trial in Geriatric Bipolar Depression

Columbia Suicide Severity Rating Scale (C-SSRS)	X	X	X	X	X	X	X	X	X	X

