Potential benefits include the possibility of immediate and sustained mood improvement following the LFMS experimental treatments over a one-week period, and the further development of an antidepressant treatment for mood and anxiety disorders. LFMS may provide immediate improvement in mood, and a successful outcome to this study may lead to its use in emergency and acute treatment situations. However, it is also possible that this study may not be directly beneficial to the subject.

IX. MONITORING AND QUALITY ASSURANCE

c. Independent monitoring of source data

A visit checklist is completed to ensure that all study procedures have been completed and documented. The study coordinator monitors all source documents to ensure that all study procedures have been completed and documented. The primary investigator will ensure that the study coordinator and clinical study staff are qualified to perform all duties delegated as outlined.

d. Safety monitoring (e.g., Data Safety Monitoring Board, etc.)

Subject safety and adverse events will be monitored and assessed by study staff during the study visit. If any events should occur, the subject can withdraw voluntarily or at the discretion of the PI.

Monitoring of the LFMS study will occur in two areas, and be primarily performed by two people. These two areas include 1) monitoring of LFMS device functions and 2) monitoring of patient information and mood assessments.

LFMS system functioning and records will be monitored by the coinvestigator, [name]. These records will consist of a weekly check of LFMS computer log files, which contain the following information:

- Date of system operation
- Subject number
- Waveform used
- System completion status (“completed” “interrupted” or “system fault”)

These log files are only accessible by [name]. These reports will be printed out and stored.

LFMS patient information will be monitored by the Study Coordinator. Data to be recorded include:

- Date of enrollment
- Subject number
- Diagnosis, if any
- Date of treatment
- Scores for mood rating scales before treatment
- Scores for mood rating scales after treatment
- Notes on any reports of side effects or sensations

Low Field Magnetic Stimulation: Initial Trial in Geriatric Bipolar Depression

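### Does the weekly check of device logs by a co-investigator break the blind?

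*Combined protocol and SAP*

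**What the plan says.** Phase 2, section IV.f (Treatment assignment, and randomization) describes a double-blind, sham-controlled trial in which sham reproduces the operating sounds, "so that the operator, rater, and subject are all blinded". It continues: "An inaccessible log file records the treatment condition, time and date of each system use for confirmation after the study is un-blinded". On allocation it says "Treatment assignments will be randomized and balanced within blocks of 10" and "The LFMS Device contains a pre-randomized folder of subject treatment links that are assigned to subjects as they arrive for their first treatment". The LFMS (Visits 3-7) procedures add that the device randomises when the subject number is entered at the first treatment visit.

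Phase 2, section IX.d (Safety monitoring) divides monitoring into two areas, handled mainly by two people. A co-investigator monitors the device: "These records will consist of a weekly check of LFMS computer log files, which contain the following information". The fields are date, subject number, waveform and completion status. Only one named person can open these files, and the reports are printed and kept. The Study Coordinator monitors patient information, including mood scores. The same section has the principal and co-investigators meet monthly to review progress, and section IX.e gives the outcome analysis to a named person and colleagues.

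Phase 1 has the same blinding and monitoring text in IV.c and IX.b.

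**The concern.** Section IV.f keeps a record of treatment condition out of reach until un-blinding, while IX.d has a log read every week that pairs each subject with a waveform. If the waveform entry differs between active and sham, a member of the investigating group can learn allocation during the trial. The blinding statement names operator, rater and subject but not investigators or analysts.

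Three consequences would follow in a bad case.

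- Data are dropped after randomisation when treatment changes ("Changes in treatment will not prompt withdrawal but will indicate that data will be excluded from analysis"), and the text does not say who applies this or whether they are blinded.
- Someone who knows past allocations in blocks of 10 can partly predict later ones, and entry to the trial needs a judgement: "Acceptance will rely on approval by one of the study physicians, in addition to satisfying all other criteria".
- An analyst who knew the arms early could be influenced in choices that section VI leaves open. Section VI.f expects the trial to give a first effect-size estimate, so the blind matters even in an exploratory study.

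**Working it through.** The plan gives no figure to reproduce here, so the first step is to compare the two descriptions.

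| | Log in IV.f | Log in IX.d |
|---|---|---|
| Contents | treatment condition, time, date | date, subject number, waveform, completion status |
| When read | after un-blinding | weekly |
| Access | described as inaccessible; to whom is not stated | one named person |

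**Same file or two?** The field lists differ: the first has condition and time of day, the second has waveform and completion status. That fits two files, though it does not prove it. 'Inaccessible' may also mean closed to operator, rater and subject, the three parties named just before.

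**Does the waveform entry show the arm?** Not stated. The device holds a link for each subject, which fits an entry coded by subject. An entry naming the active or sham waveform is also possible.

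**If it shows the arm, what could the reader affect?**

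- *Ratings.* The rater and subject are stated to be blinded. Mood-score monitoring belongs to the Study Coordinator.
- *Exclusions.* Sections V.i and the visit procedures state a rule: a treatment change means the data are excluded. Changes are asked about and noted at visits. The log reader has no stated part.
- *Acceptance.* A study physician decides before the device assigns the arm. The reader is given no part.
- *Withdrawal.* After an event this rests with the subject or the principal investigator.
- *Monthly meeting.* It covers progress and patient information reports. Device logs are not mentioned.
- *Analysis.* The names of the log reader and the analysis lead are both removed, so overlap cannot be judged.

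**Ceiling on prediction.** Assume 5:5 blocks of m = 5 per arm, an entry that shows the arm, known block boundaries, and every earlier line read before the next subject starts.

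- Assignments known with certainty per block: 2m/(m + 1) = 10/6 = 1.67 of 10.
- Correct guesses per block: 5 + (1024/252 − 1)/2 = 6.53 of 10, against 5 by chance.
- For 32 randomised (three blocks plus two): 3 × 1.67 = 5.0 certain; 3 × 6.532 + 0.500 + 0.556 = 20.65 correct, against 16.
- For 64 randomised (six blocks plus four): 6 × 1.67 = 10.0 certain; 6 × 6.532 + 0.500 + 0.556 + 0.556 + 0.595 = 41.40 correct, against 32.

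The plan's wording is "Up to 64 subjects will be enrolled in order to achieve our target of 32 completers of the treatment protocol", so 32 is a completer target and 64 an enrolment limit; the number randomised is not given. If the entry is coded, nothing is known with certainty and guessing stays at chance. Even at the ceiling, prediction biases selection only if the predictor influences who enters, and no passage says so. A weekly check also does not ensure that each line is read in time.

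**The case for a change.** The strongest opposing case is that a double-blind protocol should not leave this to inference. A log that names the waveform most naturally says what was delivered. If it is the same file as in IV.f, the protocol contradicts itself. Limiting access to one person reduces the number of people exposed but does not separate that person's duties. The limit is stated for the files, not the printouts, and the rule that stored data are open only to study staff protects confidentiality, not the blind. No sentence keeps the log reader out of the monthly meeting or the analysis, and a clarification would cost little.

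Most of this is correct as a reading of the text. The wording does leave the log reader's blinding status open, and the printouts have no stated restriction. What does not follow is that carrying out the plan as written gives a biased or weaker result. Each harmful route needs an entry that reveals the arm plus a role that no passage gives the log reader; for analysis, redaction prevents a judgement. Checking the delivered waveform is also useful in itself, since hiding the field would mean that a wrong waveform is no longer detected directly.

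**Conclusion.** No change to the plan is needed. The two sections sit awkwardly together, but the documents support no more than an unstated detail: whether the logs are separate and whether the waveform entry is coded. The team holds the device and the files and can answer both questions at once. Having one person verify delivery while someone else monitors mood scores is a workable arrangement.

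The exposure runs from 0 subjects, if the entry is coded, to one person able to sort all treated subjects by arm, if it is not. The documents do not place the truth within that range. Even at the upper end they show no rater, operator, subject or analyst losing the blind, and no acceptance or exclusion decision in the log reader's hands. The block-prediction figures are correct arithmetic for a chain of conditions that the text does not establish, so they do not measure a defect in this trial. The conclusion assumes that the stated blinding of operator, rater and subject is kept and that the treatment-change exclusion is applied as the rule it is written to be. It would need another look if the log reader proved to be both unblinded and the outcome analyst before un-blinding, which the public text cannot show.
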